## 6. Research Plan:

[figure not shown]
**6.1. Preliminary evidence:** A high plasma  $\omega$ -6: $\omega$ -3 PUFA ratio was associated with increased pain and functional limitations in middle-aged and older adults with chronic knee osteoarthritis. The study consisted of a cross-sectional analysis of 167 participants recruited from the communities surrounding the University of Florida (UF) and the University of Alabama at Birmingham (UAB) as part of the Understanding Pain and Limitations in Osteoarthritic Disease (UPLOAD) cohort. Participants were categorized as having a low or high plasma  $\omega$ -6: $\omega$ -3 ratio based on quartile splits (25th% and 75th%). Those with a high ratio reported greater pain, stiffness, and functional limitations (all  $P < 0.04$ ), and demonstrated lower physical functioning on the Short Physical Performance Battery ( $P = 0.001$ ). On experimental pain measures, those with a high ratio demonstrated higher punctate pain sensitivity at the knee and hand after 10 mechanical taps.

**6.2. Experimental Design:** This pilot will serve as a small-scale study to inform the feasibility of future large-scale trials. Feasibility is measured by metrics that indicate the ability to conduct a large-scale study, such as recruitment of the target population, retention of participants, and adherence to the intervention. This study will utilize a double-blind, randomized, placebo-controlled, repeated measures design to determine the effectiveness of krill oil supplementation on pain and physical function among older adults with chronic musculoskeletal pain (**Fig. 3**). Specifically, the design will determine whether 3 months of supplementation with krill oil will (1) reduce pain intensity and interference, (2) improve physical function, (3) increase plasma  $\omega$ -3 index (%EPA+DHA in erythrocytes) and reduce  $\omega$ -6: $\omega$ -3 ratio, and (4) reduce inflammatory markers. Eligible participants will be randomized on a 1:1 ratio to either krill oil ( $n=20$ ) or placebo ( $n=20$ ). Participants will be instructed to maintain their current dietary habits, including and

especially their consumption of  $\omega$ -3 (e.g., fatty fish) and  $\omega$ -6 PUFAs (e.g., vegetable oils), as well as their current physical activity levels.

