**Table 2. Inclusion and Exclusion Criteria**

| Inclusion   |
|---|
| 
 
• Provision of signed and dated informed consent form
 
• Stated willingness to comply with all study procedures and availability for the duration of the study
 
• Male or female, aged <math>\geq 60</math> years
 
• Exhibiting chronic musculoskeletal pain of the hip, knees, or lower back (<math>>3</math> months)
 
• Average pain <math>\geq 4</math> on a 0–10 numeric rating scale
 
• Exhibiting moderate mobility limitations (Short Physical Performance Battery score 4-10)
 
• Ability to take oral supplement and be willing to adhere to the supplementation regimen
 
• Agreement to adhere to Lifestyle Considerations (see section 6.4.d) throughout study duration
 
  |
| Exclusion   |
| 
 
• Any known coagulation or bleeding disorders
 
• Standing regimen of anticoagulants or full-dose aspirin
 
• Regular use of opioids or high-dose NSAIDs
 
• Taking medication known to affect muscle (e.g. steroids)
 
• Taking selective serotonin reuptake inhibitors (SSRIs)
 
• Omega-3 supplementation within the past 3 months
 
• High consumption of fatty fish (<math>>2</math> servings/week)
 
• Habitual supplementation with other complementary medicines/supplements that may affect the study results, including St. John's Wort
 
• Known allergy to seafood
 
• Clinically significant conditions: uncontrolled diabetes, severe cardiovascular disease, seizure disorders, uncontrolled hypertension (<math>>150/90</math>mmhg at baseline), cancer or cancer that has been in remission <math><5</math> years
 
• History of atrial fibrillation or atrial flutter
 
• Dementia
 
• History of smoking, alcohol abuse, or illicit drug use
 
• Ambulatory impairments which would limit the ability to perform physical function tests
 
• Treatment with another investigational drug or other intervention within 3 months
 
• Planning a surgical procedure during the study period
 
• Planning to permanently leave the area during the study period
 
 |

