**6.4.a. Recruitment:** Our team has substantial experience recruiting older adults with chronic pain and moderate functional impairments. Recruitment efforts will be aided by the UF Older Americans Independence Center's Clinical Research Core. Participants will be recruited from the areas surrounding the University of Florida in Gainesville/Alachua County, Florida. There are  $>284,000$  older adults ( $\geq 65$ y) residing in Alachua County, FL. If needed, recruitment will be expanded to neighboring North/Central Florida regions.

**6.4.b. Screening:** Screening for eligibility will consist of a two-step process, starting with a phone screening to assess basic eligibility criteria. If found eligible via phone screen, interested individuals will be invited to an in-person screening visit. The screening visit will collect demographic characteristics (e.g., age, race/ethnicity, education, income), anthropometric measures, as well as a comprehensive pain history and physical function testing (SPPB) to assess functional status.

**6.4.c. Randomization and blinding:** The trial will use a double-blinded design, so that participants, investigators, and assessors will be blinded to group assignments. Randomization for this study will be conducted using REDCap (Research Electronic Data

Capture), a secure, web-based application designed to support data capture for research studies. REDCap provides automated randomization to ensure unbiased allocation of participants to study groups and audit trails to maintain a detailed log of all randomization activities for transparency and reproducibility. The randomization module in REDCap will be configured to use the random block method, ensuring balanced allocation across groups.

**6.4.d. Lifestyle considerations:** During this study, participants are asked to (1) maintain their current dietary habits, especially their consumption of  $\omega$ -3 (e.g., fatty fish) and  $\omega$ -6 PUFAs (e.g., vegetable oils), (2) maintain current physical activity levels, and (3) not participate in other interventional research studies.

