**Table 3. Schedule of Activities**

| Procedures  | Screening            | Enrollment/
Baseline | Q1 Calls                      | Midpoint                  | Q3 Calls                    | Final                    |
|---|----------------------|-------------------------|-------------------------------|---------------------------|-----------------------------|--------------------------|
| Visit #
Week(s)
Duration                                    | 1
-4 to 1
1 hr | 2
1
2-3 hrs       | Phone
1-4 +/- 1
15 mins | 3
6 +/- 1
1.5-2 hrs | Phone
9 +/- 1
15 mins | 4
12 +/- 1
2-3 hrs |
| Informed consent   | X                    |                         |                               |                           |                             |                          |
| Randomization   | X                    |                         |                               |                           |                             |                          |
| Capsule count & dispensation                                      |                      | X                       |                               | X                         |                             | X                        |
| Health assessment  |                      |                         |                               |                           |                             |                          |
| Medical history/update  | X                    | X                       |                               | X                         |                             | X                        |
| Adverse events  |                      |                         | X                             | X                         | X                           | X                        |
| Vital signs   | X                    | X                       |                               | X                         |                             | X                        |
| Anthropometrics  |                      |                         |                               |                           |                             |                          |
| Height  | X                    |                         |                               |                           |                             |                          |

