- Disease progression which requires discontinuation of the study intervention
- If the participant meets an exclusion criterion (either newly developed or not previously recognized) that precludes further study participation
- Participant unable to receive krill oil for 12 weeks

Subjects who sign the informed consent form and are randomized but do not receive the study intervention may be replaced. Subjects who sign the informed consent form, and are randomized and receive the study intervention, and subsequently withdraw, or are withdrawn or discontinued from the study, will not be replaced.

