Krill Oil for Pain and Physical Function in Older Adults

NCT06580912

03/05/2025

Statistical Analysis Plan

Feasibility and acceptability will be determined as (1) recruitment of at least 80% of the target sample ($n=32$), (2) attrition rate $\leq 20\%$, and (3) adherence rate $\geq 70\%$ (based on capsule counts and intake diaries). Changes in fatty acid profile (i.e., omega-3 index) will be analyzed using mixed-effects linear regression models with fixed effects for treatment group, time (as categorical), and a group-by-time interaction. While there is currently no guidance on what may constitute a minimal clinically meaningful change in plasma ω -3 index, current evidence supports that an ω -3 index $\geq 8\%$ may be protective against cardiovascular disease, whereas an index of $\leq 4\%$ indicates increased risk⁽⁸⁸⁾. Given the pilot nature of the trial, analyses will emphasize estimation of between-group differences and corresponding 95% confidence intervals rather than formal hypothesis testing. Estimates of variability and feasibility metrics will be used to inform outcome selection and design considerations for future trials. Changes in pain intensity, pain interference, and physical function will be analyzed using mixed-effects linear regression models, with fixed effects for treatment group, time (as categorical), and a group-by-time interaction, adjusting for age, sex, and BMI. A random intercept will be included for each participant, assuming an independent covariance structure. A 20% pain reduction on a 0-10 numeric rating scale is considered a clinically significant pain reduction.¹ A 1-point change in the SPPB and a 50-m increase in the 6MWT are considered clinically meaningful changes for older adults.² All analyses will follow an intent-to-treat approach, including all randomized participants in the groups to which they were assigned, regardless of adherence. A per-protocol analysis may also be conducted as a sensitivity analysis, including only participants with $\geq 70\%$ adherence. Missing data will be addressed using maximum likelihood estimation within the mixed-effects models, which accommodates data missing at random. Sensitivity analyses may be conducted using multiple imputation if warranted.

References

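### Table 3 randomises at screening, up to about 4 weeks before first dispensing and several baseline outcomes, which creates avoidable randomised-but-undosed participants whom the protocol and SAP treat differently

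*Protocol*

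**What the plan says.** **Timing of allocation.** In Table 3 the randomisation row ("Randomization | X") is marked under Screening only. That is Visit 1, with a window of weeks -4 to 1. The next column, headed Enrollment/Baseline, is Visit 2 in week 1. The row "Capsule count & dispensation" has its first mark there. Section 6.4.c describes the REDCap block randomisation but does not say at which visit, or after which procedures, the allocation is drawn.

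**What is measured when.** The dried blood spot for the omega-3 index, WOMAC, 6MWT, handgrip, hs-CRP and IL-6/TNF-alpha all have their first mark at Visit 2. SPPB, GCPS-R, the Michigan Body Map, MoCA, height and weight have a mark at Screening.

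**Eligibility.** Section 6.2 states "Eligible participants will be randomized on a 1:1 ratio". Section 6.4.b puts a phone screen first, then a visit with "comprehensive pain history and physical function testing (SPPB) to assess functional status". One exclusion in Table 2 is tied to a later-sounding time point: "uncontrolled hypertension ( >150/90 mmhg at baseline".

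**Who is analysed.** Section 6.7 says that people who are "randomized but do not receive the study intervention may be replaced". The SAP defines its intention-to-treat analysis as "including all randomized participants in the groups to which they were assigned, regardless of adherence". Both documents set a 20% attrition limit, and neither says what it is a percentage of.

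**The concern.** If Table 3 is followed as printed, a person can be allocated weeks before receiving a capsule and before most outcome measures have a first value. Some of the people allocated may change their minds, fall ill or turn out to be ineligible before Visit 2. Drawn at Visit 2, the allocation would leave those people as screen failures. Drawn at Visit 1, it makes them randomised participants without treatment.

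Two things are then at stake. First, the protocol's replacement rule and the SAP's analysis set give different answers about the same people. Second, attrition is one of the primary feasibility criteria, and whether it is met can depend on whether undosed people are counted.

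**Working it through.** **Step 1: the plan's own figures.** Section 6.5.l gives 20 per group, 20% loss and about 16 per group remaining: 20 × (1 − 0.20) = 16. The recruitment threshold is 0.80 × 40 = 32. Both reproduce. At a limit of no more than 20% (section 6.5.l and SAP), attrition may reach 0.20 × 40 = 8 people. Table 1 words the limit as strictly below 20%, which would allow 7; I use 8.

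**Step 2: the gap.** Screening can be as early as week -4 and Visit 2 is in week 1. If the calendar has no week 0, the longest gap is 4 weeks; if it has one, 1 − (−4) = 5 weeks. The screening window also extends to week 1, so the shortest gap is 0.

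**Step 3: what a person lost in the gap contributes.** Maximum likelihood in a mixed model uses every participant with at least one record of the outcome in question. Someone lost before Visit 2 has:
- no record of omega-3 index, WOMAC or 6MWT, and so contributes nothing to those models;
- a screening record of SPPB and GCPS-R, and so can enter models of those outcomes.

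**Step 4: size, under an assumed loss rate.** The documents give no rate of loss between Visits 1 and 2. Let x be that share, and take 5%, 10% and 15% as an illustrative range.

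- Without replacement: lost before dosing = 40x; dropouts still allowed = 8 − 40x.
- With replacement until 40 are dosed: number randomised N = 40 / (1 − x), rounded up; never dosed = N − 40. If 8 of the 40 dosed then drop out, attrition is 8/40 = 20% of the dosed and (8 + N − 40)/N of the randomised.

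| x (assumed) | Lost of 40, no replacement | Dropouts still allowed | Randomised, with replacement | Never dosed | Total loss over randomised |
|---|---|---|---|---|---|
| 5% | 2 | 6 | 43 | 3 | 11/43 = 25.6% |
| 10% | 4 | 4 | 45 | 5 | 13/45 = 28.9% |
| 15% | 6 | 2 | 48 | 8 | 16/48 = 33.3% |

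In each of these rows the trial meets the 20% limit if attrition is counted over the dosed and fails it if counted over the randomised.

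**Step 5: after the change.** With allocation at Visit 2, just before dispensing, the scheduled gap is 0 and the randomised and dosed sets nearly coincide. The figures 40, 20, 16 and 32 do not change.

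**The case against.** The strongest reply is that the mark is probably a slip. Visit 2 is headed Enrollment/Baseline, section 6.2 says that it is eligible people who are randomised, and the gap may be zero for many participants. That may be so. But section 6.4.c does not correct the table, and Table 3 is the only place that assigns randomisation to a visit, so it has to be corrected or justified either way.

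A reader might infer more from the table than the documents support. Four such inferences should be set aside:

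- **That eligibility as a whole follows allocation.** Most criteria can be settled at the phone screen or Visit 1 through medical history, pain history, GCPS-R and SPPB, and Table 3 does not give the order of procedures within a visit. The one doubtful item is the blood-pressure exclusion. Even there, the protocol uses the word baseline loosely: section 6.5.d places height at baseline, while Table 3 marks it at Screening only. Blood pressure is taken at both visits.
- **That intention-to-treat analysis becomes impossible.** People can still be analysed as allocated, and SPPB and GCPS-R have screening values. The gap in the data is confined to outcomes first measured at Visit 2.
- **That allocation could influence the later baseline measures.** Section 6.4.c blinds participants, investigators and assessors, section 6.3 describes a matched placebo, and no capsule has yet been taken. This risk is weak and the point does not rest on it.
- **That the loss is known to be 2-6 people.** That range is an assumption.

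It is also fair to say that the conflict between replacement and the analysis set would exist wherever the mark stood. Early randomisation enlarges the group to which the conflict applies, so moving the mark alone would not be a complete repair.

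**Conclusion.** The point stands in a limited form. As written, the schedule allows allocation from 0 to about 4 weeks (5 if there is a week 0) before first dispensing and before the first measurement of the omega-3 index, WOMAC, 6MWT, handgrip and inflammatory markers. The blood-pressure exclusion may also fall after allocation, depending on what baseline means. People lost in that interval have no record for the Aim 2 omega-3 analysis or for two of the Aim 3 outcomes. Section 6.7 permits their replacement, whereas the SAP includes them.

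Under an assumed 5-15% loss, 2-6 of 40 are affected. The attrition criterion could then be met or failed according to a denominator that neither document names. The timing, the conflict between the two rules and the missing denominator come straight from the documents. The number of people affected does not, and it could be zero.

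**What to change.** 1. In Table 3, move the randomisation mark from Screening to Visit 2.
2. In section 6.4.c, state that the REDCap allocation is drawn once eligibility has been confirmed and the baseline assessments and blood draws are complete, immediately before dispensing.
3. In Table 2, say which visit's blood-pressure reading the exclusion refers to, so that it can be seen to precede allocation.
4. Reconcile the replacement rule in section 6.7 with the SAP's analysis set. State that anyone randomised stays in that set whether or not replaced, and how a randomised person with no record of a given outcome is reported.
5. In section 6.5.l and the SAP, state that attrition is counted over all randomised participants.

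The cost is one table cell and a few sentences. No visit is added, the sample size stays at 40, and SPPB keeps its pre-randomisation value from Screening. The one practical burden is that staff must draw the allocation during Visit 2.

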| Common Data Elements (CDEs)                                       | X                    |                         |                               |                           |                             |                          |
| Pain history  | X                    |                         |                               |                           |                             |                          |
| Michigan Body Map   | X                    |                         |                               |                           |                             | X                        |
| Graded Chronic Pain Scale-Revised (GCPS-R)                        | X                    | X                       |                               | X                         |                             | X                        |
| Western Ontario and McMaster Universities Arthritis Index (WOMAC) |                      | X                       |                               | X                         |                             | X                        |
| PainDETECT  |                      | X                       |                               |                           |                             | X                        |
| Patient Global Impression of Change (PGIC)                        |                      |                         | X                             | X                         | X                           | X                        |
| Medicine Acceptability Questionnaire (MAQ)                        |                      |                         |                               | X                         |                             | X                        |
| Pepper Assessment Tool for Disability (PAT-D)                     |                      | X                       |                               | X                         |                             | X                        |
| Fear Avoidance Beliefs Questionnaire (FABQ)                       |                      | X                       |                               |                           |                             | X                        |
| Pain Self-Efficacy Questionnaire (PSEQ)                           |                      | X                       |                               |                           |                             | X                        |

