#### 6.5.f. Pain.

- A Pain History will be obtained, including an assessment of painful bodily locations/distribution (with the Michigan Body Map), etiology of pain (if identifiable), duration, character and quality of pain, and aggravating and alleviating factors.
- The Graded Chronic Pain Scale (GCPS) is a 7-item questionnaire that measures pain intensity and interference over the last 1, 3, or 6 months. Scores can be used to classify participants on a Chronic Pain Grade: pain-free (grade 1), low disability and low intensity (grade 2), low disability, high intensity (grade 3), high disability, moderately limiting (grade 4), and high disability, severely limiting (grade 5).
- The Western Ontario and McMaster Universities Arthritis Index (WOMAC) is a well-validated and widely utilized measure of pain symptoms and physical disability. It is comprised of 24 items to evaluate three domains: pain, stiffness, and physical function. Responses can be summated for domain-specific scores, as well as a global score.
- The PainDETECT will be used to determine the presence of neuropathic pain.
- Movement-evoked pain (MEP) refers to the pain during activity, which is a primary driver of musculoskeletal pain. MEP will be assessed immediately after each physical task using a 101-point numerical rating scale, with 0 corresponding to “no pain” and 100 to “the most intense pain imaginable.”

**6.5.g. Disability.** The Pepper Assessment Tool for Disability (PAT-D) is a validated, 23-item instrument measuring 5 domains of function in older adults: mobility, transferring, upper extremity, activities of daily living (ADL), and instrumental activities of daily living (IADL).

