**6.5.I. Sample size and statistical approach:** This pilot study is designed as a small-scale test to guide the design and implementation of large-scale studies to evaluate the effectiveness of krill oil supplementation among older adults with chronic musculoskeletal pain. We will enroll 40 older adults who will be randomly assigned (1:1) to either krill oil ( $n=20$ ) or placebo ( $n=20$ ) for a 3-month trial duration. Approximately 16 participants per group after a 20% loss to follow-up is expected to provide sufficient data to indicate the feasibility of a larger study and to provide descriptive estimates of effects. **Aim 1.** Feasibility and acceptability will be determined as (1) meeting at least 80% of the recruitment goal ( $n=32$ ), (2) no more than 20% attrition, and (3) treatment acceptance and adherence ( $\geq 70\%$  consumption of prescribed doses and increased blood  $\omega$ -3 index). **Aim 2.** Mean changes in  $\omega$ -3 index and  $\omega$ -6: $\omega$ -3 ratio will be evaluated with paired-samples T-tests for within-group difference and independent-samples T-tests for between-group difference. An intention-to-treat approach will be used for between-group analyses. While there is currently no guidance on what may constitute a minimal clinically meaningful change in plasma  $\omega$ -3 index, current evidence supports that an  $\omega$ -3 index  $\geq 8\%$  may be protective against cardiovascular disease whereas an index of  $\leq 4\%$  indicates increased risk. Similarly, an  $\omega$ -6: $\omega$ -3 ratio of 4:1 or lower is considered optimal for health. Baseline and 3-month levels of the  $\omega$ -3 index and the  $\omega$ -6: $\omega$ -3 ratio will be compared against these benchmarks. **Aim 3.** Due to the repeated-measures design, we will use mixed-effects linear regression models to evaluate changes in pain intensity and functional interference (WOMAC), as well as changes in objective measures of physical function (SPPB, 6MWT). Fixed effects will be specified for the treatment group, time (in weeks), and a group\*time interaction effect. An independence covariance matrix structure will be assumed with a random intercept for each participant included. A 20% pain reduction on a 0-10 numeric rating scale is considered a clinically significant pain reduction. A 1-point change in the SPPB and a 50-m increase in the 6MWT are considered clinically meaningful changes for older adults.

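### The SAP's pain model does not adjust for pre-dose pain and makes no provision for the second pre-dose GCPS-R score, so its pain intervals are probably wider than the collected data allow

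*Protocol*

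**What the plan says.** Protocol Table 3 marks the row "Graded Chronic Pain Scale-Revised (GCPS-R") at Screening, Enrollment/Baseline (Visit 2), Midpoint (week 6) and Final (week 12). The row "Capsule count & dispensation" is first marked at Visit 2, so the first two GCPS-R scores come before any capsule can act. In the same table "Western Ontario and McMaster Universities Arthritis Index (WOMAC") has one pre-dose mark, at Visit 2.

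Protocol 6.5.f says of the GCPS that it "measures pain intensity and interference over the last 1, 3, or 6 months". The Aim 3 text in the Protocol's sample size and statistical approach section instead says that the mixed model will "evaluate changes in pain intensity and functional interference (WOMAC").

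The SAP says: "Changes in pain intensity, pain interference, and physical function will be analyzed using mixed-effects linear regression models". The fixed effects are group, "time (as categorical), and a group-by-time interaction, adjusting for age, sex, and BMI", with a random intercept per participant. It names no pain instrument, defines no baseline, and does not list the visits that make up time.

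**The concern.** The SAP puts its weight on between-group estimates and 95% confidence intervals, so the width of those intervals is the main product of the pain analysis. In a random-intercept model with group, categorical time and their interaction, the week-12 effect is in essence a difference in mean change from one pre-dose level. A change score uses baseline pain with a fixed coefficient of one, not as a predictor with an estimated coefficient, and so leaves removable variance in the contrast. Age, sex and BMI are constant within a person and do little for a within-person contrast.

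If GCPS-R is the analysed scale, a second pre-dose score also exists and the plan gives it no role. With about 16 people per arm, a free reduction in standard error is worth having. Fixing the baseline definition before unblinding also removes a later choice between two scores.

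**Working it through.** **Inputs from the documents.** 20 randomized per arm; 20% loss to follow-up; random intercept; categorical time; GCPS-R at four visits, two of them pre-dose. The plan's own figures reproduce: 20 × (1 − 0.20) = 16 per arm, and 0.80 × 40 = 32.

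**Assumptions (not in the documents).** Pain has SD 1 at each visit. ρb is the correlation of the Visit 2 score with week 12, ρs that of Screening with week 12, and r that between the two pre-dose scores. With 16 per arm, SE = √(F × 2/16), where F depends on the analysis. Half-widths use t(30) = 2.042.

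**Step 1: the SAP contrast.** F = 2(1 − ρb).
- ρb = 0.5: F = 1.00, SE = 0.354 SD, half-width 0.722 SD.
- ρb = 0.7: F = 0.60, SE = 0.274 SD, half-width 0.559 SD.

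Making Screening a fourth level of time, with Visit 2 as reference, leaves both SEs unchanged (0.354 and 0.274), because the extra level has its own mean in each arm. So under three or four levels the second score adds nothing.

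**Step 2: adjust for one pre-dose score.** F = 1 − ρb². The SE ratio to the SAP contrast is √[(1 − ρb²)/(2(1 − ρb))] = √[(1 + ρb)/2].
- ρb = 0.3: 0.806; 0.5: 0.866; 0.7: 0.922; 0.8: 0.949.

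This is a cut of about 5% to 19%. Constraining the arms to a common pre-dose mean gives the same result: SE 0.306 at ρ = 0.5 and 0.252 at ρ = 0.7.

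**Step 3: add the Screening score.**
- Mean of the two as covariate: F = 1 − [(ρb + ρs)/2]² / [(1 + r)/2].
- Both as separate covariates: F = 1 − (ρb² + ρs² − 2rρbρs)/(1 − r²).

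| ρb | ρs | r | F, SAP | F, Visit 2 only | F, mean | F, separate | SE of mean vs Visit 2 only | SE of separate vs Visit 2 only |
|---|---|---|---|---|---|---|---|---|
| 0.3 | 0.3 | 0.3 | 1.40 | 0.910 | 0.862 | 0.862 | −2.7% | −2.7% |
| 0.5 | 0.5 | 0.5 | 1.00 | 0.750 | 0.667 | 0.667 | −5.7% | −5.7% |
| 0.7 | 0.7 | 0.7 | 0.60 | 0.510 | 0.424 | 0.424 | −8.9% | −8.9% |
| 0.8 | 0.8 | 0.8 | 0.40 | 0.360 | 0.289 | 0.289 | −10.4% | −10.4% |
| 0.5 | 0.5 | 0.9 | 1.00 | 0.750 | 0.737 | 0.737 | −0.9% | −0.9% |
| 0.6 | 0.5 | 0.8 | 0.80 | 0.640 | 0.664 | 0.639 | +1.8% | −0.1% |
| 0.7 | 0.6 | 0.9 | 0.60 | 0.510 | 0.555 | 0.505 | +4.3% | −0.5% |
| 0.8 | 0.7 | 0.9 | 0.40 | 0.360 | 0.408 | 0.358 | +6.4% | −0.3% |

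The second score is worth most when both scores predict week 12 equally well and share little error. Overlapping recall raises r. If Screening also predicts less well, the mean does harm and separate entry gains almost nothing. Against the SAP contrast, adjusting for the mean ranges from 22% better (first row: √(0.862/1.40) = 0.784) to 1% worse (last row: √(0.408/0.40) = 1.010).

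**Step 4: cost in degrees of freedom.** Adjusting for q covariates in N = 32 inflates the variance on average by 1 + q/(N − q − 3).
- q = 1: 1 + 1/28 = 1.036, SE up 1.8%.
- q = 2: 1 + 2/27 = 1.074, SE up 3.6%.

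Net of that, the gain from one pre-dose score is about 18% at ρb = 0.3 (0.806 × 1.018 = 0.820) and about 3% at ρb = 0.8 (0.949 × 1.018 = 0.966).

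**The case against.** **The instrument may be WOMAC.** The only instrument the Protocol ties to this model is WOMAC, which is measured once before dosing. Section 6.5.f also describes the GCPS, while Table 3 schedules the GCPS-R. This stands: the part about a second score applies only if GCPS-R is analysed. It does not touch baseline adjustment, which applies to either scale. The SAP's wording (intensity and interference) fits the 6.5.f description of the GCPS at least as well as WOMAC, so the ambiguity itself needs settling.

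**The SAP is silent rather than wrong.** A reader might infer that the SAP has decided to discard one of two GCPS-R scores. It says nothing either way, since it defines neither baseline nor the levels of time. What can be said is that its listed covariates do not include pre-dose pain, and that neither a three-level nor a four-level reading of time draws on the extra score.

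**Averaging might look like a free 13%.** With equal correlations, change from the mean of two scores has variance ratio 1.5/2 = 0.75 to change from one, an SE cut of 13.4%. That compares two change scores and assumes that the pre-dose scores are equally good replicates. The two visits are at most about five weeks apart and recall covers at least one month, so the scores may share error. Pain of at least 4 is also an entry criterion. Against adjustment for Visit 2 alone, the mean can lose.

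**Allocation precedes Visit 2.** Table 3 places randomization in the Screening column. The trial is double-blind, capsules are first dispensed at Visit 2, and recall covers at least a month, so the Visit 2 score can hardly reflect treatment.

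**Intention to treat.** Modelling only weeks 6 and 12 as responses drops anyone without a follow-up score, which sits badly with the SAP's commitment to include all randomized participants. This is a fair objection, and the common-mean form of the model answers it.

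**Pain is exploratory.** It is listed as tertiary/exploratory, and no feasibility decision turns on its interval. This limits the importance of the point.

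**Conclusion.** The point holds as a minor matter of efficiency and specification. The plan's contrast is valid, and nothing here suggests bias. Under assumed correlations of 0.3 to 0.8, adjusting for one pre-dose pain score cuts the SE by about 5% to 19%, or about 3% to 18% after the cost of the covariate. Most of the available gain lies there.

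The second GCPS-R score adds about 0% to 9% at correlations up to 0.7 (10.4% at 0.8), before its own cost of about 2%. A simple mean can be 2% to 6% worse than Visit 2 alone. The documents therefore do not support a claim that using both scores is sure to help, or that a fixed share of precision is being lost. All these sizes are large-sample figures for 16 per arm and rest on correlations that the documents do not give.

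**What to change.** In the SAP:
1. Name the instrument for pain intensity and for pain interference, and reconcile it with the Protocol's Aim 3 text (WOMAC) and section 6.5.f (GCPS).
2. Define baseline and list the visits that form time.
3. Adjust for pre-dose pain. Either model weeks 6 and 12 as responses with pre-dose pain as covariate, or keep the pre-dose score as a response and constrain the arms to a common pre-dose mean. The second form keeps all randomized participants in the likelihood.
4. For GCPS-R, enter the Visit 2 and Screening scores as separate covariates, or use their mean if they are expected to predict follow-up equally well. If both are kept as responses, an unstructured covariance avoids forcing equal weight on them. For WOMAC, use its single baseline score.

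The cost is a few sentences before unblinding and one or two degrees of freedom, each worth about 2% of the SE at 32 participants. No new data or visits are needed.
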